#### **17.8.2 Reporting Adverse Events of Special Interest**

Not applicable.

### **17.9 Follow-up for Adverse Events**

All AEs resulting in the patient's discontinuation and SAEs will be followed up until they are resolved or closed.

Resolution of an AE is defined as the return to pre-treatment status or stabilisation of the condition with the expectation that it will remain chronic.

The Investigator must respond to any request for follow-up information (e.g. additional information, outcome and final evaluation, specific records where needed) and answer any question that Sponsor or designee may have regarding the AE.

Regarding SAEs, the timelines and procedure for follow-up reports are the same as those for the initial reports for SAEs.

This is necessary to permit a prompt assessment of the event by the Sponsor or designee and (as applicable) to allow the Sponsor to meet strict regulatory timelines associated with expedited safety reporting obligations.

If follow-up information on SAEs is available, a follow-up e\_CRF form will be completed by the Investigator and sent to the CRO as above-described, under [Section 17.8.1](#).

### **17.10 Pregnancy**

Patients must be instructed that known or suspected pregnancy occurring during the study should be confirmed and reported to the Investigator, who must then withdraw the patient from the study without delay. The Investigator should also be notified in case the partner of a male study subject becomes pregnant at any time during the course of the study (in this event a specific ICF for the subject's partner will be obtained).

In the event that a patient is subsequently found to be pregnant after inclusion in the study, then pregnancy will be actively followed up to the term and the status of mother and child will be reported by the Investigator to the CRO through the appropriate pregnancy report provided by the CRO.

The Investigator will send pregnancy reports to the CRO according to the timeframes stated for SAEs ([Section 17.8.1](#)), with follow-up information to be actively sought for the outcome of pregnancy.

If pregnancy results in abnormal outcome that the investigator and/or the Sponsor considers to be due to the IMP, this will be treated as an expedited ADR report.

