#### **4.2.2 *Toxicology***

Safinamide did not exert pathophysiological relevant effects on the function of the cardiovascular, respiratory, renal and gastrointestinal system nor of the central nervous system.

Retinal degeneration was observed in repeated-dose studies in rat but not in monkey studies. However, these changes have not been noted in any human or non-human primate species despite detailed investigations having been performed for extended periods of time.

Treatment with safinamide was associated with effects on female fertility, embryo-foetal development and post-natal development in rats and rabbits. Fertile women have been excluded from clinical studies with safinamide unless practising adequate contraception.

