## 7.2 Duration of Clinical Trial

Study participation will be up to a maximum duration of 18 weeks and will comprise a screening period (up to 2 weeks), a treatment period (16 weeks) and a 1-week telephone follow-up.

The start of the study is defined as the date of the first visit of the first patient participating in the study.

The end of the study is defined as the date of the last visit of the last patient participating in the study.

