### 8.2 Selection of Patients

#### 8.2.1 *Inclusion Criteria*

Patients can be included in the study if they meet all inclusion criteria listed below:

1. Male or female patients aged  $\geq 18$  years old.
2. Chinese ethnicity.
3. Able to understand and willing to provide written informed consent.
4. Able to maintain an accurate and complete 24-hour diary with the help of a caregiver.
5. Diagnosis of idiopathic Parkinson's Disease (IPD) using the United Kingdom Parkinson's Disease Society Brain Bank criteria of more than 3 years duration.
6. Be levodopa responsive and receiving treatment with stable daily doses of oral L-dopa (including controlled release [CR], immediate release [IR] or a combination of CR/IR), with and without benserazide/carbidopa, with or without addition of a catechol-O-methyltransferase (COMT) inhibitor and may be receiving concomitant treatment with stable doses of dopamine agonists, anticholinergics and/or amantadine for at least 4 weeks prior to the screening visit.
7. A Hoehn and Yahr stage between 1-4 inclusive during the "ON" phase.
8. Experiencing motor fluctuations with a minimum of 1.5 hours/day of "OFF" time during the day (excluding morning akinesia), based on historical data.
9. If female, be post-menopausal for at least one year or have undergone hysterectomy or, if of child-bearing potential, must have a negative pregnancy test, must not be breast-feeding nor become pregnant during the study and must use adequate contraception for 1 month prior to randomisation and for up to 1 month after the last dose of study drug. Adequate contraception is defined as:
  - a) Hormonal oral, implantable, transdermal, or injectable contraceptives or a non-hormonal intrauterine device or female condom with spermicide or contraceptive sponge with spermicide or diaphragm with spermicide or cervical cap with spermicide for at least 1 month prior to randomization.
  - b) a male sexual partner who agrees to use a male condom with spermicide or a sterile sexual partner.

For all women of child-bearing potential, urine pregnancy test result at screening must be negative.

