### **9.3 Telephone Follow-up**

A telephone follow-up call will be performed 1 week after the end of treatment for safety reasons. The following assessments and procedures will be performed as detailed in the Study Flow Chart ([Section 29.0, Appendix 1](#)):

- Recording of concomitant medications and therapies.
- Recording of AEs.

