**TABLE 1 CLINICAL LABORATORY EVALUATIONS**

| Haematology:   |                                    |           |
|---|------------------------------------|-----------|
| Haemoglobin   | Platelet count                     |           |
| Haematocrit   | Red blood cell count               |           |
| White blood cell count and absolute differential (neutrophils, lymphocytes, monocytes, eosinophils and basophils) |                                    |           |
| Clinical Chemistry:  |                                    |           |
| Urea or BUN   | Alkaline phosphatase (ALP)         | Chloride  |
| Creatinine  | Alanine aminotransferase (ALT)     | Sodium    |
| Bilirubin (direct and total)  | Aspartate aminotransferase (AST)   | Calcium   |
| Uric acid   | Gamma-glutamyltranspeptidase (GGT) | Potassium |
| Pregnancy Tests:   |                                    |           |
| Dipstick - urine pregnancy test at visit 1 (screening) and visit 6 (week 16/EOT/ET)                               |                                    |           |

An estimate of the total blood volume to be taken from each patient during scheduled study visits (visits 1 and 6) is summarized in [Table 2](#).

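### Section 17.10 sets no pregnancy-reporting window after the last dose: contraception runs for 1 month, but the last planned contact is at 1 week, and partner pregnancies have no backstop

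*Protocol*

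**What the plan says.** Section 4.2.2 gives the background: "Treatment with safinamide was associated with effects on female fertility, embryo-foetal development and post-natal development in rats and rabbits". It adds that fertile women have been kept out of safinamide studies unless they used contraception. Section 8.2.1, criterion 9, says that a woman of child-bearing potential "must use adequate contraception for 1 month prior to randomisation and for up to 1 month after the last dose of study drug".

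Section 17.10 contains three relevant provisions:

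- **Patients:** "Patients must be instructed that known or suspected pregnancy occurring during the study should be confirmed and reported to the Investigator". The investigator must then withdraw the patient from the study.
- **Partners:** the investigator should be told if the "partner of a male study subject becomes pregnant at any time during the course of the study".
- **Follow-up:** if "a patient is subsequently found to be pregnant after inclusion in the study, then pregnancy will be actively followed up to the term". The outcome for both mother and infant then goes to the CRO. No end date is attached.

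Section 17.10 also applies the SAE timeframes of Section 17.8.1 to pregnancy reports.

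On contact after treatment, Section 9.3 says "A telephone follow-up call will be performed 1 week after the end of treatment for safety reasons"; its listed content is concomitant treatment and adverse events. Section 7.2 describes participation as screening plus "a treatment period (16 weeks) and a 1-week telephone follow-up". Under Section 10.1.5 and Table 1, the last urine pregnancy test is at Visit 6 (week 16, end of treatment or early termination).

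**The concern.** The protocol sets a period after dosing in which pregnancy is to be avoided, but its reporting text does not refer to that period. The instruction to patients and the partner clause are both tied to the study. For an individual patient, planned contact stops about 1 week after treatment.

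A pregnancy that begins in the rest of the contraception month, or one that began earlier and is recognised only then, comes to light when no one is scheduled to ask about it. Whether it is reported depends on the patient volunteering it. What is at stake is the completeness of outcome data on the reproductive risk that the protocol itself describes.

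**Working it through.** There is no stated figure to reproduce. The check sets the passages side by side and uses calendar arithmetic.

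**Inputs.** Contraception to 1 month after the last dose (Section 8.2.1, criterion 9), taken as 28 to 31 days. Last contact 1 week after treatment (Section 9.3), at Day 119 ±3 in the flow chart. End-of-treatment visit at Day 112 ±3. SAE reportability to a call or visit 2 weeks ±3 days after the last dose (Section 17.8.1). SAEs spontaneously reported within 30 days of the last dose are also reported and followed (Section 10.1.7). Half-life 20 to 24 hours (Section 4.2.1).

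**Step 1: contraception period left after the last contact.** Formula: days of contraception minus day of the call.

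- 28 − 7 = 21 days
- 30 − 7 = 23 days
- 31 − 7 = 24 days

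The visit tolerances move the call relative to the end-of-treatment visit: from 116 − 115 = 1 day to 122 − 109 = 13 days after it.

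**Step 2: could the SAE window serve instead?** Section 17.10 borrows the timeframes of Section 17.8.1. If that were read as borrowing the 2-week window:

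- Nominal shortfall: 28 − 14 = 14 to 31 − 14 = 17 days
- With the ±3-day tolerance: 28 − 17 = 11 to 31 − 11 = 20 days

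The 2-week contact is also not in the schedule; the only call is at 1 week. The 30-day figure would nearly match the contraception month (31 − 30 = 1 day short at most), but Section 10.1.7 applies it to SAEs and Section 17.10 does not cite it.

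**Step 3: what does *the study* mean in Section 17.10?** The only defined end is the last visit of the last patient (Section 7.2). Other wording points to a patient-level meaning. Criterion 9 separates pregnancy in the study from the month after the last dose. Exclusion 15 separates the study from the 2 weeks after the last dose. Section 7.1 has patients instructed at the study's end. Section 17.10 pairs the report with withdrawal, which cannot apply to someone who has finished. On the trial-level reading, the window would depend on enrolment date: many months for the first patient and about 1 week for the last. Neither reading gives the month in criterion 9 to every patient.

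**Step 4: how much exposure falls in the uncovered days?**

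- Five half-lives: 5 × 20/24 = 4.2 days to 5 × 24/24 = 5.0 days
- Fraction left at day 7: 0.5^(168/20) = 0.3% to 0.5^(168/24) = 0.8%

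Conceptions with material exposure therefore fall mainly on treatment or in the first week after it. The uncovered days matter mostly for when such pregnancies are recognised.

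**Step 5: number of patients.** The protocol does not give the share of women of child-bearing potential. Assuming 1 to 5% of the 306 to be randomised: 0.01 × 306 ≈ 3 to 0.05 × 306 ≈ 15 women. Partners of male patients are additional and not counted. These are women at risk, all required to use contraception; they are not expected pregnancies.

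**The case against.** The strongest reply is that Section 17.10 does not close reporting when the patient leaves. Its follow-up provision covers any patient found to be pregnant after inclusion, with no end date. A conception on treatment also occurs during the study, whenever it is recognised. Both points stand. A reader might infer that late pregnancies are not reportable, or that conceptions in the last treatment weeks are lost because the Visit 6 test is too early to show them. The text does not support either inference: a negative test at Visit 6 limits detection, not the duty to report.

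The reply leaves two things open. The follow-up provision binds the investigator only after learning of the pregnancy and does not ask the patient to tell anyone. It also speaks only of patients, so nothing equivalent covers partners.

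It is also fair to say that the short half-life leaves little drug on board beyond day 7, and that the protocol does not say why it chose 1 month; the link to the animal findings is an inference. The case for alignment therefore rests on consistency with the protocol's own period, not on demonstrated exposure throughout it. The consent pages are not in the material reviewed and may carry further instructions.

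A reader might also see a parallel gap at entry, because the only test before dosing is at screening. Nothing is contradicted there: criterion 9 asks for a negative test at screening, contraception is already required for 1 month before randomisation, and eligibility is rechecked at Visit 2.

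**Conclusion.** The point holds as a mismatch of windows. Section 17.10 gives no reporting period after the last dose, and 21 to 24 days of the contraception period have no planned contact and no clear instruction to report. This takes 1 month as 28 to 31 days and the call at its nominal day. For patients, late pregnancies may go unreported, but any that become known must still be reported and followed. For partners of male patients there is no such backstop, and the gap is clearest there.

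The practical size is small: perhaps 3 to 15 women on an assumed 1 to 5%, plus an unknown number of partners. No efficacy analysis or sample-size figure is affected. It is a wording correction worth making because it is nearly free and improves safety capture.

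**What to change.** In Section 17.10, replace *during the study* (patients) and *during the course of the study* (partners) with one explicit window, aligned with the contraception period in criterion 9, that is, to 1 month after the last dose. Criterion 9 sets no period for male patients, so the partner window has to be stated in its own right. Extend the follow-up and reporting sentence to partner pregnancies, subject to the partner consent already foreseen in that section.

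Give the instruction at the end-of-treatment or early-termination visit (Section 9.2.3) and repeat it at the existing call (Section 9.3). Reconcile the pregnancy window with the 1-week call (Section 9.3), the 2-week SAE window with its unscheduled contact (Section 17.8.1), and the 30-day SAE window (Section 10.1.7).

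The cost is a few words and one reminder at contacts already planned, with no new visit or test. The downside is that some reports will arrive after the patient's last scheduled contact, so sites and the CRO must be able to receive them.

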## 18.0 RESPONSIBILITIES

The clinical conduct of this study will be overseen by the CRO. The CRO Medical Monitor will be responsible for daily medical monitoring, including safety monitoring. The specific responsibilities of the CRO are detailed in the relevant study agreement.

### 18.1 Responsibilities of the Sponsor (or delegated CRO)

Responsibilities of the Sponsor include the following:

- Select qualified Investigators.
- Provide each Investigator with the last approved SmPC for the authorised product.
- Submit clinical trial application/notification to the concerned Competent Authorities (CA) involved in the clinical trial.
- Prepare and submit to the EC/CA all the pertinent documentation needed for approvals.
- Implement and maintain quality assurance (QA) and quality control (QC) system with written SOPs to ensure the studies are conducted and data are generated, documented (recorded), and reported in compliance with the CTP, GCPs, and the applicable regulatory requirements.
- Promptly act in case of non-compliance by an Investigator or by members of the Sponsor or CRO.
- Ensure that the IMP is manufactured in accordance with any applicable GMP, is coded and labelled in a manner that protects blinding, if applicable, and labelling complies with applicable regulatory requirements.
- Supply the Investigators/Institutions with the IMP(s).
- Appoint appropriate trained Clinical Trial Monitor(s).
- Ensure the ongoing safety evaluation of the IMP.
- Promptly submit all Suspected Unexpected Serious Adverse Reactions (SUSARs) or other safety issues requiring expedited reporting to ECs and CAs in accordance with local or international regulations and take appropriate measures necessary to safeguard study patients.
- Promptly notify all concerned Investigators, the ECs and the CAs of findings that could adversely affect the health of patients, impact on the conduct of the study, or alter the EC/CA authorisation to continue the study.
- When the study is completed or prematurely terminated, prepare or ensure preparation of a comprehensive Clinical Trial Report (CTR) for regulatory purposes.
- Prepare and submit to ECs and CAs safety updates and Development Safety Update Reports, as applicable.
- Secure agreement from all involved parties to ensure direct access to all study related centres, source data/documents, and reports for the purpose of monitoring and auditing by the sponsor, and inspection by domestic and foreign regulatory authorities.

- Provide adequate treatment/compensation for patients in the event of trial-related injury in accordance with the applicable regulatory requirements.
- Provide indemnity for the Investigator in accordance with [Section 25.0](#) of this CTP.
- Terminate the Investigator's/Institution's participation in case of non-compliance.
- Promptly inform the Investigators/Institutions, the CAs and the ECs of premature termination or suspension of a study and the reason(s) for the termination or suspension.
- Designate appropriately qualified medical personnel who will be readily available to advise on study-related medical questions or problems. If necessary, outside consultant(s) may be appointed for this purpose.

## **18.2 Responsibilities of the Clinical Trial Monitor**

The Sponsor has engaged the services of a CRO to perform all monitoring functions within this clinical study. CRO's monitors will work in accordance with CRO's SOPs, with the exception of the use of the "Adverse Event Form for immediate reporting" provided by the Sponsor.

The Clinical Trial Monitor is the principal communication link between the Sponsor/CRO and the Investigator. Responsibilities of the Clinical Trial Monitor include to:

- Train the Investigator(s) on all applicable SOPs, guidelines and regulations concerning the clinical evaluation of an IMP, including the safety reporting, and ensure a deep understanding of the CTP, the reporting requirements and responsibilities.
- Act according to predetermined SOPs, visit the Investigator periodically to verify adherence to the CTP and assure that all data are correctly and completely recorded. In order to perform his/her role effectively.
- Ensure that the trial site has adequate space, facilities, equipment, lab and staff.
- Ensure that all staff assisting the Investigator in the trial have been adequately informed about the details of the trial, verifying that the Investigator follows the approved CTP and all amendment(s), if any, and that they are performing the specified activities and procedures and have not delegated these functions to unauthorised individuals.
- Verify that informed consent has been obtained and recorded from all the patients prior to their participation to the trial.
- Aid the Investigator and at the same time the Sponsor/CRO, in the maintenance of complete, legible, well-organised and easily retrievable data.
- Inform the Investigator of any eCRF entry error, omission or illegibility. The Clinical Trial Monitor should also ensure that appropriate corrections, additions, or deletions are made, dated, explained (if necessary), and initialled by the Investigator;
- Check that the storage, dispensing, administering, returning of IMPs are safe, handled in accordance with local regulations as well as study requirements and Sponsor/CRO SOPs. All those activities have to be adequately documented.
- Assist the Investigator in any notification procedure of SAE within 24h and verify the seriousness of the AEs.

- Submit promptly to the Sponsor/CRO a written monitoring report after each site visit and written documentation of all relevant telephone calls, letters and other contacts with the Investigator.
- Verify that the Investigator is maintaining the essential documents (Investigator's file) up to end of study and for the required period.

### **18.3 Responsibilities of the Investigator**

Responsibilities of the Investigator include to:

- Ensure that he/she has sufficient time to conduct and complete the trial; nominate adequate staff and has appropriate facilities.
- Submit an up-to-date curriculum vitae and GCP trainings and awareness of GCPs to the Sponsor/CRO and to EC/CA.
- Agree and sign the CTP with the Sponsor confirming that he/she will work according to the CTP and GCPs and procedures as stated in the paragraph 18.2; assist monitoring and permit auditing.
- Follow the submission of notification/application to EC jointly with the Sponsor/CRO, where appropriate.
- Provide information to all staff members involved with the trial.
- Be thoroughly familiar with the appropriate use of the IMP(s) as described in the SmPC, protocol and any other information sources provided.
- Fully inform trial patients about the clinical trial and obtain their informed consent.
- Certify that all IMP(s) have been correctly delivered, stored, and safely handled, and that reconciliation of IMPs will be done at the end, after any discrepancies are justified.
- Follow the trial randomisation procedure and ensure that the code is broken only in accordance with the CTP.
- Collect, record, and report data properly.
- Notify the Sponsor/CRO within 24h in the case of SAE and take appropriate measures to safeguard patients.
- Promptly report to EC and Sponsor changes increasing the risk to patients and/or affecting significantly the conduct of the trial and new information that may affect adversely the safety of the patients or the conduct of the trial.
- Agree with and sign the Clinical Study Report of the trial, if requested.
- Ensure that the confidentiality of study patients personal data is respected by all persons involved as per laws in force.
- Keep the information supplied by the Sponsor as strictly confidential.
- Make all data available for direct access to the Sponsor/CRO personnel (e.g.: Clinical Trial Monitor, Auditor), EC or CAs for validation/audit/review/inspection purposes.
- Ensure that in the patient medical records it is clearly evident that the patient is participating in the clinical trial.
- Inform the family doctor, with patient's consent, about patient's participation in the trial.

- Provide a list of appropriately qualified persons (Site Signature/Delegation Log) to whom the Investigator has delegated some duties relevant to the conduct of the trial, together with their signatures and initials.
- Provide patients enrolled in the study with a card bearing information that he/she is participating in a clinical study, and where contact addresses/telephone numbers are reported.
- Submit, during the trial, on regular basis, written summaries of the trial status to the EC, when requested.

